7.1.5.1. Statistical Methodology Specification

Primary Statistical Analysis
Endpoint / Variables

 Proportion of participants with plasma HIV-RNA greater than or equal to 50 copies/mL at Month 12 (OLI and BIK)/Month 11 (D2I) per Snapshot algorithm for the mITT-E population.
Snapshot Dataset

 Virologic outcome (“HIV-RNA <50” or “≥ 50 c/mL”) per Snapshot algorithm is determined by the last available on-treatment HIV-1 RNA measurement within the analysis visit window of interest (refer to analysis window defined in Section 16.3). In addition, participants who discontinue for reasons not related to adverse event with on-treatment HIV-1 RNA result at the time of discontinuation ≥ 50 c/mL or who change study treatment not permitted per protocol during Maintenance Phase before the analysis visit are classified as ‘HIV-RNA ≥ 50 c/mL’. Full details of the Snapshot algorithm are provided in Appendix 9: Snapshot Algorithm Details
Model Specification

 The primary efficacy endpoint will be analysed using a stratified analysis with Cochran-Mantel-Haenszel (CMH) weights, adjusting for the randomization strata BMI (<30, ≥ 30 kg/m²) and Gender at Birth (female, male)

- The CMH estimate of the adjusted treatment difference will be calculated as a weighted average of strata-specific estimates of the treatment difference calculated within each stratum as follows:
 - Baseline BMI < 30 kg/m² and Male Gender at Birth
 - Baseline BMI < 30 kg/m² and Female Gender at Birth
 - Baseline BMI ≥ 30 kg/m² and Male Gender at Birth
 - Baseline BMI ≥ 30 kg/m² and Female Gender at Birth

- If n_k is the number of CAB LA + RPV LA (Q2M) treated participants, m_k is the number of BIK arm treated participants, and $N_k = n_k + m_k$ is the total number of participants in the k^{th} stratum, then the CMH estimate is given by

$$\hat{d}_{cmh} = \frac{\sum W_k \hat{d}_k}{\sum W_k}$$

where

$$W_k = \frac{n_k m_k}{N_k}$$

are CMH weights and \hat{d}_k are estimates of the differences in proportions between the two treatment arms, p_{Q2M} and p_{BIK} , for the k^{th} stratum.

- The corresponding two-sided 95% CI will be calculated as

$$\hat{d}_{cmh} \pm 1.96 \times \sqrt{\hat{\text{var}}(\hat{d}_{cmh})}$$

where the variance estimator [Sato, 1989] consistent in both sparse data and large strata is given below

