16.4.3. Treatment State

Within each treatment study phase (i.e. Maintenance, and Extension—based on assignment of study phase described in Section 16.4.1), only those assessments which occur within the ranges shown below will be considered ‘on-treatment’ for the given phase. Note “on-treatment” criteria will not be implemented for adverse event summaries.

Table 7 Treatment State within Study Phases

Study Phase ^a	Treatment State	Date Range
Screen	Pre-treatment	All assessments/events within Phase
Maintenance	On-treatment	Q2M Arm: Date ≤ max (Date of Last Injection Dose + 67, Date of Last Oral Dose + 1)
		BIK Arm: Date ≤ Maintenance ART Stop Date + 1
	Post-treatment	Q2M Arm: Date > max (Date of Last Injection Dose + 67, Date of Last Oral Dose + 1)
		BIK Arm: Date > Maintenance ART Stop Date + 1
Extension	On-treatment	Date ≤ max (Date of Last IP Injection Dose + 67, Date of Last Oral Dose + 1)
	Post-treatment	Date > max (Date of Last IP Injection Dose + 67, Date of Last Oral Dose + 1)
Long-Term Follow-up	On-treatment	Date ≤ min (LTFU ART start date, max (Date of Last IP Injection Date + 67, Date of Last Oral Dose + 1))
	Post-treatment	Date > min (LTFU ART start date, max (Date of Last IP Injection Date + 67, Date of Last Oral Dose + 1))
Note: 
 Treatment State is determined after data has been assigned to the study Phases as defined in Section 16.4.1 		

- The upper bound with last IP injection / last oral dose /Maintenance ART Stop Date should only be applied to participants who permanently discontinue from study treatment
- Date = Assessment/Start Date.
- Last oral dose may be CAB/RPV or SOC ART Oral Bridging where CAB/RPV is not available due to COVID-19.

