16.9. Appendix 9: Snapshot Algorithm Details

Detailed Algorithm Steps

- Consider an analysis visit window for Month X as defined in Section [16.3.1](#)
- The HIV-1 RNA threshold of 50, 200 copies/mL will be analysed, respectively, in this study.
- The COVID-19 pandemic presents significant logistical challenges for many clinical sites around the world, with variable restrictions being placed on site resources and operations, and on an individual participant's ability to attend clinic visits. The snapshot algorithm is modified to allow for the presentation of full scope of COVID-19 relatedness. The analysis window 'Week 48' and HIV-1 RNA threshold of '50 c/mL' are used for the purpose of illustration. A participant's Snapshot response and reason at Week 48 are categorized as below.
 - HIV-1 RNA < 50 c/mL
 - HIV-1 RNA ≥ 50 c/mL
 - Data in window not below threshold
 - Non-COVID-19 related
 - Discontinued for lack of efficacy
 - Discontinued for other reason while not below threshold
 - Change in background therapy*
 - COVID-19 related
 - Discontinued for lack of efficacy
 - Discontinued for other reason while not below threshold
 - Change in background therapy*
 - No Virologic Data at Week 48 Window
 - Non-COVID-19 related
 - Discontinued study due to AE or death
 - Discontinued study for other reasons
 - Not evaluated or discontinued due to confirmed pregnancy**
 - On study but missing data in window
 - COVID-19 related
 - Discontinued study due to AE or death
 - Discontinued study for other reason
 - On study but missing data in window

- Note: since permanent changes in ART are not permitted in this protocol, all such participants who permanently change ART will be considered 'HIV-1 RNA \geq 50 c/mL' if the change is made prior to an analysis timepoint. Participants with protocol permitted oral bridging treatment, CAB+RPV or SOC (during COVID-19 pandemic due to the unavailability of the CAB/RPV IM injections and oral CAB+RPV), or a temporary change in ART by mistake prior to an analysis timepoint (e.g. participant took the ART different from study treatment during oral lead-in by mistake for a short period of time and then went back to the study treatment) will not be considered 'HIV-1 RNA \geq 50 c/mL' due to 'change in ART'.
- The steps in determining response and reasons are indicated in Table below, in the order stated.

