- *Background therapy is not given to participants while on study. The "change in background therapy" in detailed steps below refers to the "change in ART" in this study.
- ** This category is not needed if no subject on the Q2M arm becomes pregnant and continues in the study.

Detailed steps

Please note that the following scenarios will NOT be penalized per Snapshot algorithm (i.e. please exclude these scenarios from **Conditions** 1-4).

- Dose reduction, dropping a component, or change in formulation (e.g. 'Tivicay + Kivexa' to 'Triumeq' with the identical ingredients)
- Protocol permitted temporary oral bridging, or temporary change in ART by mistake

Condition ('Week 48' indicates Week 48 window)	Response	Reasons
1. If non-permitted change in background therapy prior to Week 48		
○ not due to COVID-19	HIV-1 RNA \geq 50	Change in background therapy (non-COVID-19 related)
○ due to COVID-19	HIV-1 RNA \geq 50	Change in background therapy (COVID-19 related)
2. If permitted change^[a] in background therapy prior to Week 48 AND the latest on-treatment VL prior to/on the date of change is \geq 50 c/mL (NA to this study)		
○ not due to COVID-19	HIV-1 RNA \geq 50	Change in background therapy (non-COVID-19 related)

○ due to COVID-19	HIV-1 RNA \geq 50	Change in background therapy (COVID-19 related)
3. If non-permitted change in background therapy during Week 48		
○ Last on-treatment VL during Week 48 prior to/on the date of change \geq 50 c/mL	HIV-1 RNA \geq 50	Data in window not below 50
○ Last on-treatment VL during Week 48 prior to/on the date of change < 50 c/mL	HIV-1 RNA < 50	
○ No VL during Week 48 prior to/on the date of change and the change in background therapy is not due to COVID-19	HIV-1 RNA \geq 50	Change in background therapy (Non-COVID-19 related)
○ No VL during Week 48 prior to/on the date of change and the change in background therapy is due to COVID-19	HIV-1 RNA \geq 50	Change in background therapy (COVID-19 related)
4. If permitted change^[a] in background therapy during Week 48 AND the last on-treatment VL prior to/on the date of change is \geq 50 c/mL (NA to this study)		
4.1 This last on-treatment VL occurs prior to Week 48		
• The change in background therapy is not due to COVID-19	HIV-1 RNA \geq 50	Change in background therapy (non-COVID-19 related)
• The change in background therapy is due to COVID-19	HIV-1 RNA \geq 50	Change in background therapy (COVID-19 related)

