4.2 This last on-treatment VL occurs during Week 48 but prior to/on the date of change	HIV-1 RNA \geq 50	Data in window not below 50
5. If none of the above conditions met		
5.1 On-treatment VL available during Week 48		
• Last on-treatment VL during Week 48 \geq 50 c/mL	HIV-1 RNA \geq 50	Data in window not below 50
• Last on-treatment VL during Week 48 < 50 c/mL	HIV-1 RNA < 50	
5.2 No on-treatment VL during Week 48		
5.2.1 If participants are still on study, i.e. a participant has not permanently discontinued the study treatment yet, or if a participant permanently discontinued		

the study treatment and the upper bound of analysis snapshot window is prior to the following date:
 
For Q2M arm: Min[max(Date of last CAB/RPV LA Dose + 67, Date of last oral dose+1), withdrawal date]
 
For BIK arm: Min (BIK Stop Date + 1, withdrawal date)
 
Note:
 
 • Last oral dose: may be CAB/RPV or SOC ART Oral Bridging where CAB/RPV is not available due to COVID-19 impact. • Withdrawal Date: date the participant failed to complete per corresponding conclusion form 		

5.2.1.1 If no on-treatment VL during Week 48 is not due to COVID-19
		

 • If no on-treatment VL is not due to confirmed pregnancy 	
No virologic data at Week 48 Window
	
On study but missing data in window (Non-COVID-19 related)

 • If no on-treatment VL is due to confirmed pregnancy (“while on-treatment”: data not evaluable) 	
No virologic data at Week 48 Window
	
Not evaluated or discontinued due to confirmed pregnancy(Non-COVID-19 related)

5.2.1.2 If no on-treatment VL during Week 48 is due to COVID-19
	
No virologic data at Week 48 Window
	
On study but missing data in window (COVID-19 related)

5.2.2 If participants withdraw before/during Week 48 due to
		

5.2.2.1 Non-COVID-19 related safety reasons (e.g. AE/death, liver chemistry stopping criteria, renal toxicity withdrawal criteria, QTc withdrawal criteria etc, as recorded in eCRF Conclusion form)
	
No virologic data at Week 48 Window
	
Disc due to AE/death (Non-COVID-19 related)

5.2.2.2 COVID-19 related safety reasons (e.g. AE/death, liver chemistry stopping criteria, renal toxicity withdrawal criteria, QTc withdrawal criteria etc, as recorded in eCRF Conclusion form)	No virologic data at Week 48 Window	Disc due to AE/death (COVID-19 related)

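### The Snapshot steps exempt a dropped component from the change-in-ART failure rule, which conflicts with the SAP's other statements of the primary endpoint when a Q2M participant permanently omits CAB or RPV

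*SAP*

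**What the plan says.** The SAP states the rule on treatment changes in several places.

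- **Section 7.1.5.1 (primary analysis).** Participants "who change study treatment not permitted per protocol during Maintenance Phase before the analysis visit are classified as" HIV-RNA ≥50 c/mL. Section 7.1.4 says the same of non-permitted changes before the analysis window. Neither section exempts a dropped component. Section 7.1.5.1 refers to Appendix 9 for full details.
- **Appendix 9, note before the detailed steps.** It says that "since permanent changes in ART are not permitted in this protocol, all such participants who permanently change ART will be considered" HIV-1 RNA ≥50 if the change precedes the analysis timepoint. Its only exceptions are permitted oral bridging and a temporary change made by mistake.
- **Appendix 9, detailed steps.** Programmers are told that "the following scenarios will NOT be penalized per Snapshot algorithm (i.e. please exclude these scenarios from" Conditions 1 to 4. The first scenario listed is "Dose reduction, dropping a component, or change in formulation", illustrated by a switch from Tivicay plus Kivexa to Triumeq.
- **Appendix 9, footnote.** "Background therapy is not given to participants while on study"; in this study the term stands for a change in ART.
- **Appendix 1, Per-Protocol category 03.** Permanent changes of ART regimen are kept in the Per-Protocol Snapshot analysis as ≥50.
- **Section 16.4.3, Table 7.** Q2M on-treatment status in the Maintenance Phase is "Date ≤ max (Date of Last Injection Dose + 67, Date of Last Oral Dose + 1"). This upper bound applies only to participants who permanently discontinue study treatment.

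**The concern.** The exemption reads like text carried over from a trial with a background regimen. Its example involves neither study regimen, and only the formulation part of it fits that example. Conditions 2 and 4 are marked as not applicable to this study, but the exemption was not adapted in the same way. With no background therapy, the only component that can be dropped is a study drug. Q2M consists of two separately injected drugs and BIK is one tablet, so this part of the exemption bears mainly on Q2M.

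What is at stake is whether such a participant is a failure in the primary endpoint. Two programmers following different parts of the SAP could reach different answers. The more lenient answer lowers the Q2M failure count, which favours non-inferiority in an open-label trial, and it also credits the participant as a responder in the key secondary endpoint.

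**Working it through.** The SAP states no figure for this point, so the check is a trace through the algorithm followed by a sizing.

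**Trace.** Take a Q2M participant who permanently omits CAB or RPV before the Month 11/12 window and stays on study.

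1. Following the detailed steps, the case is exempt, so Conditions 1 to 4 are skipped and Condition 5 applies.
2. If an on-treatment viral load exists in the window, Condition 5.1 decides. "Last on-treatment VL during Week 48 < 50 c/mL" gives HIV-1 RNA <50. A last value of 50 or more gives HIV-1 RNA ≥50, which is a failure despite the exemption.
3. If there is no viral load in the window, Condition 5.2.1 gives no virologic data. That is outside the ≥50 numerator but is not a <50 response.
4. Table 7 does not require that both drugs were given. Receiving one drug alone does not, as written, take the participant off treatment.
5. Following the Appendix 9 note instead, an omission read as a permanent change in ART gives ≥50 whatever the viral load.

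The two routes differ only in steps 2 (value below 50) and 3. The case that is credited as <50 is the one with a measured in-window value below 50.

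**Planned sensitivity analyses (Section 7.1.5.1).** The ITT-E and all-data-as-observed analyses use the same steps. Per-Protocol category 02 can exclude participants with at least 10% of time under-dosed at Month 12, case by case. That removes a participant but does not count one as a failure.

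**Size per participant.** Section 2.3 plans about 654 participants randomised 2:1.

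- Q2M: 654 × 2/3 = 436; BIK: 654 − 436 = 218.
- One participant: 1/436 = 0.23 percentage points.
- Without the 11 participants of the excluded site, assuming they split 2:1: (654 − 11) × 2/3 ≈ 429, and 1/429 = 0.23 points.
- The margin is 4 points (Section 2.4).

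**Effect on the confidence limit.** I used the SAP's CMH difference and Sato variance with a single stratum, 436 versus 218. The failure rates are assumptions, since the SAP gives none. With n = 436, m = 218, N = 654, W = nm/N = 145.33, and x, y the failures in Q2M and BIK:

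- d = x/n − y/m
- P = [n²y − m²x + nm(m − n)/2]/N²
- Q = [x(m − y)/N + y(n − x)/N]/2
- upper limit = d + 1.96 × √(dP + Q)/W

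At an assumed 1% in both arms, x = 4 and y = 2. Then d = 0, Q = (4 × 216/654 + 2 × 432/654)/2 = 1.321, and the upper limit is 1.96 × √1.321/145.33 = 1.55%.

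If Q2M participants are reclassified from <50 to ≥50:

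| Reclassified | Upper 95% limit |
|---|---|
| 0 | 1.55% |
| 1 | 1.84% |
| 2 | 2.13% |
| 5 | 2.99% |
| 9 | 4.10% |

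Number needed before the limit first reaches 4%, by assumed rate:

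| Assumed rate | Starting failures (Q2M, BIK) | Number needed | Upper limit |
|---|---|---|---|
| 0.5% | 2, 1 | 10 | 4.07% |
| 1% | 4, 2 | 9 | 4.10% |
| 2% | 9, 4 | 6 | 4.08% |
| 3% | 13, 7 | 6 | 4.17% |

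**The case against.** The strongest reply is that there is no contradiction. Section 7.1.5.1 speaks of changes the protocol does not permit and defers to Appendix 9 for detail. The Appendix 9 note speaks of permanently changing ART. Neither mentions dropping a component, so the detailed steps could be read as defining what counts as a change. This has some force for the main text. It is weaker within Appendix 9, because the note lists its own exceptions and a dropped component is not among them.

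A second reply is that the design prevents the case. Under Section 2.3, anyone who has received an injection and discontinues the CAB LA + RPV LA regimen goes to Long-term Follow-up on suppressive HAART. What remains is a participant kept on one drug in departure from that rule. This stands as a reason to expect few cases, but it does not say how to classify one.

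A third reply is that measured suppression is a defensible basis for classification. That is arguable, but it is not what the note says.

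Three stronger readings are tempting and should not be drawn:

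- **That anyone left on one drug counts as a success.** Only a measured in-window value below 50 is credited, as the trace shows.
- **That exempting dose reduction is an equal contradiction.** Appendix 1 treats reduced dosing, including an injection below full volume, as non-compliance under category 02, and handles ART changes separately under category 03. Leaving dose reduction out of the change-in-ART conditions is consistent with that.
- **That the exemption is written for Q2M alone.** Its wording covers both arms. Only the dropped-component part bears mainly on Q2M, because BIK is a single tablet.

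**Conclusion.** The point holds as a conflict between classification rules. For permanent omission of CAB or RPV with a viral load below 50 in the window, the detailed steps of Appendix 9 give <50, while the Appendix 9 note, Sections 7.1.4 and 7.1.5.1, and Per-Protocol category 03 point to ≥50. This assumes that permanent omission of one of the two drugs is a permanent or non-permitted change in ART, which the SAP should state. No planned sensitivity analysis counts such a participant as a failure.

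The likely effect is small: 0.23 percentage points per participant, with 6 to 10 needed to lose non-inferiority at assumed failure rates of 0.5% to 3%. A reader might infer that the non-inferiority conclusion depends on this exemption. The SAP does not support that, since it gives no count of such cases and its design rule makes them unlikely. It should be corrected because the primary endpoint needs one unambiguous rule and the lenient reading favours the test arm.

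**What to change.** In the detailed steps of Appendix 9, limit the component and formulation exemption to a change of formulation with identical ingredients. Keep the permitted oral bridging and temporary mistakes already listed. State that permanent omission of CAB or RPV is a change in ART, classified under Conditions 1 and 3, so that the steps agree with the Appendix 9 note, Sections 7.1.4 and 7.1.5.1, and Per-Protocol category 03.

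Do not declare dose reduction a change in ART. Say instead that under-dosing is handled by the compliance rules in Appendix 1, category 02.

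This concerns outcome classification only, not how any participant should be treated. It costs a sentence or two of SAP wording and no new data, with possibly a slightly higher Q2M failure count. The planned listings of exposure and of dosing errors (Appendix 15) should show whether any such participant exists.

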7.1.4. Strategy for Intercurrent (Post-Randomization) Events

As defined by the Snapshot algorithm, HIV-RNA ≥ 50 copies/mL is determined by the last available on-treatment HIV-1 RNA measurement within the analysis visit window of interest.

Participants without evaluable HIV-RNA data for the visit of interest and who discontinue treatment for reasons not related to adverse event while having HIV-1 RNA ≥ 50 copies/mL at time of discontinuation, or who change study treatment not permitted per protocol prior to the analysis window are classified as having HIV-RNA ≥ 50 copies/mL.

A “while on-treatment” strategy will be implemented when a Q2M subject becomes pregnant on study but is allowed to continue. Viral load data collected after confirmed pregnancy will not be evaluated for summary tables and statistical analysis in the primary analysis. Additional sensitivity analysis including all observed data may be performed to assess consistency. See [Appendix 13: Data Handling for Pregnant Subjects](#) for details.

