5.2.2.3 Non-safety and Non-COVID-19 related reasons (e.g. Lack of efficacy, protocol deviation, withdrew consent, loss to follow-up, study closed/terminated, investigator discretion etc, as recorded in eCRF Conclusion Form)		

 ◦ Last on-treatment VL <50 c/mL OR no on-treatment VL available during study 		

 • Withdrew not due to pregnancy 	No virologic Data at Week 48 Window	Disc for other reasons (Non-COVID-19 related)

 • Withdrew due to pregnancy 	No virologic Data at Week 48 Window	Not evaluated or discontinued due to confirmed pregnancy(Non-COVID-19 related)

 ◦ Last on-treatment VL ≥ 50 c/mL AND withdrawal due to Lack of efficacy 	HIV-1 RNA ≥ 50	Disc. for lack of efficacy (Non-COVID-19 related)

 ◦ Last on-treatment VL ≥ 50 c/mL AND withdrawal due to all other non-safety related reasons 	HIV-1 RNA ≥ 50	Disc. for other reason while not below 50 (Non-COVID-19 related)
5.2.2.4 Non-safety and COVID-19 related reasons (e.g. protocol deviation, withdrew consent, loss to follow-up, study closed/terminated, investigator discretion etc., as recorded in eCRF Conclusion Form)		

 • Last on-treatment VL <50 c/mL OR no on-treatment VL available during study 	No virologic Data at Week 48 Window	Disc for other reasons (COVID-19 related)

 • Last on-treatment VL ≥ 50 c/mL AND withdrawal due to Lack of efficacy 	HIV-1 RNA ≥ 50	Disc. for lack of efficacy (COVID-19 related)

 • Last on-treatment VL ≥ 50 c/mL AND withdrawal due to all other non-safety related reasons 	HIV-1 RNA ≥ 50	Disc. for other reason while not below 50 (COVID-19 related)

 • Excluding permitted change in background therapy where change or decision to change is made prior to/on the first on-treatment viral result 		

Examples from FDA guidanceData in Window

Virologic outcome should be determined by the last available measurement while the patient is on treatment and continued on trial within the time window:

- HIV-RNA = 580 copies/mL at Day 336, HIV-RNA below 50 copies/mL on Day 350. This should be categorized as HIV-RNA below 50 copies/mL.

No Data in Window

Discontinued study due to Adverse Event or Death:

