Q2M subjects who became pregnant on study will be allowed to continue study treatment whereas BIK subjects will be withdrawn. HIV-1 RNA data will be treated as non-evaluable after confirmed pregnancy date as recorded on the eCRF, if a pregnant Q2M subject is allowed to continue.

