16.13. Appendix 13: Data Handling for Pregnant Subjects

The SOLAR study allows pregnant subjects on the Q2M arm to continue CAB LA + RPV LA treatment, while those who became pregnant on the BIK arm will be withdrawn. To minimize bias, for summary tables, if Q2M subjects continue while being pregnant, data after date of confirmed pregnancy (as recorded in the eCRF EOS pregnancy form) will not be evaluable for pregnant Q2M subjects with documented evidence confirming pregnancy unless the confirmation occurs prior to or on the same day as termination of pregnancy (as recorded on the EOS pregnancy form and the AE form, respectively) within the same time period between two study visits. The above data handling strategy will not be implemented on the following:

- All adverse events
- ECG/QTc analysis
- Vital signs
- eC-SSRS
- [REDACTED]
- Health Outcomes
- Virology

Note all observed data collected for all pregnant subjects will be included in the listings.

For study outcomes based on the FDA snapshot algorithm, an additional sub-category will be added under “No Virologic Data”: Not evaluated or discontinued due to confirmed pregnancy. Viral load after confirmed pregnancy of a Q2M subject will not be evaluated for snapshot outcomes (See [Appendix 9: Snapshot Algorithm Details](#)).

Sensitivity analysis including all data (all data as observed) will be provided for the following snapshot-based analysis is applicable:

- Summary of Study Outcomes (50 c/mL threshold)
- Summary of Analysis for Proportion of Subjects with Plasma HIV-1 RNA ≥ 50 c/mL (or < 50 c/ml)
- Proportion of Subjects with Plasma HIV-1 RNA ≥ 50 c/mL (or < 50 c/ml) by Visit

If no Q2M subject became pregnant on study, then the “while on-treatment” strategy will not be necessary and therefore no sensitivity analysis will be performed, and the additional sub-category mentioned above will not be needed.

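### For pregnant participants with a last evaluable viral load of 50 c/mL or more and no evaluable in-window result, the primary Snapshot scores a continuing Q2M participant as missing data but a withdrawn BIK participant as a failure

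*SAP*

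**What the plan says.** Appendix 13 of the SAP lets pregnant Q2M participants stay on treatment, "while those who became pregnant on the BIK arm will be withdrawn". Because of that difference, Sections 5.5.1 and 7.1.4 and Appendix 13 adopt a while-on-treatment strategy whose declared purpose is to limit bias. Appendix 9 implements it for a pregnant Q2M participant who continues: "HIV-1 RNA data will be treated as non-evaluable after confirmed pregnancy date as recorded on the eCRF".

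When there is no on-treatment viral load in the window, Appendix 9 takes two routes.

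- Step 5.2.1 opens with "If participants are still on study, i.e. a participant has not permanently discontinued the study treatment yet". Under it, step 5.2.1.1 has the row "If no on-treatment VL is due to confirmed pregnancy". The response is no virologic data, and no condition is placed on the last earlier viral load.
- Step 5.2.2.3 covers withdrawal for reasons that are neither safety nor COVID-19 related. Its row "Withdrew due to pregnancy" also gives no virologic data, but it sits under the condition that the last on-treatment viral load was below 50 c/mL or that none exists. If the last value was 50 c/mL or more, the row ending "AND withdrawal due to all other non-safety related reasons" applies, and the response is HIV-1 RNA >=50. That row has no exception for pregnancy.

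Section 7.1.4 agrees with the second route. It counts as failures those "who discontinue treatment for reasons not related to adverse event while having HIV-1 RNA" at or above 50 copies/mL at discontinuation.

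**The concern.** A rule brought in to offset an arm-specific design feature should give the same outcome for the same virological history. This one does not where the last evaluable viral load is 50 c/mL or more. The failure stays in the BIK count, while the matching Q2M participant moves to the missing-data category, which does not count towards the primary endpoint. The difference Q2M - BIK is then lower than it would be under equal scoring, and that difference decides both the non-inferiority test and the superiority test that follows it.

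The viral load cut-off is also uneven. Section 5.5.1 words it generally but refers to Appendix 13, which ties it to Q2M, as do Section 7.1.4 and Appendix 9. For BIK, Section 16.4.3 keeps results on-treatment up to one day after the stop date, so a BIK sample drawn after confirmation can still be used.

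**Working it through.** The SAP gives no figure for this point, so there is none to reproduce. The check is a trace of the algorithm, followed by a calculation of size.

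**Trace.** Pregnancy confirmed before or during the window, no evaluable in-window viral load, no change of ART.

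| Last evaluable viral load | Q2M, continues on study | BIK, withdrawn for pregnancy |
|---|---|---|
| <50 c/mL or none | No virologic data (5.2.1.1) | No virologic data (5.2.2.3) |
| >=50 c/mL | No virologic data (5.2.1.1) | HIV-1 RNA >=50 (5.2.2.3) |

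The arms part only in the second row.

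**Size per participant.** Section 2.3 gives about 654 randomised 2:1.

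- Q2M: 654 x 2/3 = 436. One failure not counted is 1/436 = 0.23 points.
- BIK: 654/3 = 218. One failure counted is 1/218 = 0.46 points.
- After removal of the 11 participants named in Section 2.1, 643 remain, about 429 and 214. The figures become 0.23 and 0.47 points.

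**Effect on the confidence limit.** I used the variance formula in Section 7.1.5.1 with a single stratum: upper limit = d + 1.96 x sqrt[(d x P + Q)/W^2], with n = 436, m = 218 and W = 436 x 218/654 = 145.33. The background failure rate is my assumption: 1%, that is 4 and 2 events. I add one affected participant per arm.

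- As written, 4/436 against 3/218: d = -0.46 points, P = -23.33, Q = 1.648, variance = (0.107 + 1.648)/21,122 = 0.0000831, upper limit 1.33%.
- Both scored >=50, 5/436 against 3/218: d = -0.23 points, P = -23.44, Q = 1.810, variance = (0.054 + 1.810)/21,122 = 0.0000883, upper limit 1.61%.
- Both scored as no data, 4/436 against 2/218: d = 0.00 points, upper limit 1.55%.

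Over assumed background rates of 0.5% to 3%, with one affected participant per arm, equal scoring raises the estimate by 0.23 points (both >=50) or 0.46 points (both no data). It raises the upper limit by about 0.14 to 0.33 points. The highest upper limit in this range, under any of the three scorings at 436 and 218, is 2.60%, against the margin of 4%.

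**The case against.** The strongest defence is that step 5.2.1.1 is ordinary Snapshot practice. Appendix 9 reproduces an example in which an on-study participant with a result of 50 copies/mL or more on Day 280 and nothing in the window is classed as missing. That is the general convention, and a fix that simply carried an earlier value forward for someone on study would conflict with it. The defence does not excuse the inequality, however. In the example no window result exists; here one may exist and is set aside by an arm-specific rule. What stands is that the fix must be framed as treating pregnancy as discontinuation in both arms.

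A reader might infer that a pregnant Q2M participant without an evaluable in-window result can never count as a failure. The SAP does not support that. If she withdraws for a non-safety reason with a last value of 50 c/mL or more, 5.2.2.3 scores her as in BIK, and a non-permitted ART change scores >=50 under conditions 1 and 3. An in-window result obtained before confirmation is still used under 5.1.

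A reader might also infer that the pregnancy rule always favours Q2M. It does not. Step 5.1 takes the last evaluable in-window value, and Appendix 2 (note m) schedules a retest within 4 weeks for raised Month 11/12 results. If pregnancy is confirmed between a raised result and a suppressed in-window retest, the retest is set aside and a Q2M failure is added. On the key secondary endpoint, setting aside suppressed results counts against Q2M. A BIK value drawn after confirmation may be suppressed or raised.

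Partial protection is planned. The All Data as Observed analysis restores the Q2M values, and listings show individual outcomes and HIV-1 RNA. Neither equalises the scoring in the primary analysis.

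**Conclusion.** The concern holds for one cell of the primary Snapshot: pregnancy confirmed before or during the window, no evaluable in-window viral load, and a last evaluable value of 50 c/mL or more. In that cell a continuing Q2M participant and a withdrawn BIK participant receive different outcomes. The difference favours Q2M on the primary endpoint and contradicts the rule's own purpose.

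The practical effect is small. The cell needs pregnancy and viraemia together in a population suppressed at screening. The SAP gives no expected number of pregnancies and allows for there being none on Q2M. The size figures rest on about 654 participants in a 2:1 ratio and, for the confidence limits, on my assumed background rates. A changed non-inferiority conclusion is unlikely. The correction is worth making because the flaw lies in the algorithm for the primary endpoint and costs little to remove.

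**What to change.** 1. In Appendix 9, for the primary analysis only, classify a continuing Q2M participant with confirmed pregnancy and no evaluable in-window viral load as if discontinued for pregnancy on the confirmation date, and route her through 5.2.2.3. A last evaluable value below 50 c/mL, or none, gives no virologic data; a value of 50 c/mL or more gives HIV-1 RNA >=50. State that the Day 280 convention for on-study missing data does not apply to her.
2. In Appendix 13, and to match in Section 7.1.4, apply the confirmed-pregnancy cut-off for viral load to both arms, keeping the existing exception for termination of pregnancy.
3. Keep All Data as Observed as the sensitivity analysis.

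Extending the missing-data outcome to the BIK row for values of 50 c/mL or more would also equalise the arms. It would, however, remove failures recorded before pregnancy and depart from Section 7.1.4, so it is the weaker choice.

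The cost is about two lines of text, and the Q2M failure count may become slightly less favourable. If the Month 12 analysis has already been run, report how many participants fall in this cell and give the result under equal scoring alongside it. This concerns scoring only; no clinical rule on continuing or withdrawing treatment in pregnancy is proposed.
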